3 STUDY DESIGN

3.1 OVERALL DESIGN

The current study will test the efficacy of a 12-month multi-level, Interactive Voice Response system-supported physical activity intervention vs. a waitlist control condition. Primary endpoints are changes in moderate intensity or greater aerobic physical activity from baseline to 6 months and 12 months. Secondary endpoints include examining effects on physical performance and related psychosocial variables; intervention costs, changes in physical activity from 12-18 months, potential mediators/moderators of intervention efficacy, and barriers and facilitators to the implementation and sustainability of the DIAL intervention. This two armed randomized controlled trial will enroll a sample of 240 underactive adults from rural Black Belt (Marengo, Choctaw, Sumter, Hale, Greene, Dallas) counties in Alabama. Interested individuals will attend study information sessions hosted by local county coordinators to learn more about the study and complete brief screening interviews.

If still eligible and interested, participants will complete the informed consent process and be scheduled for an assessment visit. At this visit, participants will complete measurements (height, weight, waist circumference, 2 Minute Step Test, psychosocial surveys in REDCap) at a community location with their local county coordinator. Accelerometers will be distributed with instructions and a live demonstration of proper wear. Trained UAB staff will coordinate accelerometer data collection (device initialization, delivery, maintenance, etc). Participants will wear the accelerometer for 7 days. Once valid wear protocol is confirmed, participants will complete 7-Day Physical Activity Recall interviews by phone with trained, blinded UAB research

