4 STUDY POPULATION

4.1 INCLUSION CRITERIA

Eligibility criteria include adults who are >18 years old, insufficiently active (engaging in moderate-vigorous physical activity< 60 minutes per week), residents of participating rural Black Belt (Marengo, Choctaw, Sumter, Hale, Greene, Dallas) counties, BMI 18.5-45, no serious medical condition that would make physical activity unsafe (history of heart disease, myocardial infarction, angina, stroke, or orthopedic conditions which limit mobility), not planning to move from the area within the next 18 months, able to speak and read English, willing to be randomized to either study arm and adhere to study protocol, and able to regularly access a telephone (own a cell phone or work/home landline) to complete IVR calls.

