8.2 SAMPLE SIZE DETERMINATION

Results from our previous UAB pilot study indicated an increase in minutes of moderate-to-vigorous physical activity among the DIAL intervention group compared with the control group. The SD of this measure was 90 minutes. Assuming a mean difference of 35 (SD 90) minutes in moderate-to-vigorous physical activity between the two groups from baseline to 6 months, a two-tailed two-group t test, and a significance level of 5%, we will have 80% power to detect this difference (with an effect size of 0.388) with 105 participants per arm (210 for the study). Assuming a mean change of 35 (SD 90) minutes in moderate-to-vigorous physical activity from baseline to 6 months for the intervention group, a two-tailed paired t test, and a significance level of 5%, we will have 80% power to detect this within-group change (with an effect size of 0.276) with 105 participants. Allowing for 15% attrition, we will recruit 240 participants (120 per arm).

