8.3.2 ANALYSIS OF THE PRIMARY EFFICACY ENDPOINT(S)

The primary method of analysis for physical activity, anthropometrics, and psychosocial measures, all of which will be measured at baseline, 6 months, 12 months, and 18 months, will be mixed model repeated measures analyses. Other general linear mixed model techniques may also be used. These analyses will allow us to examine changes from baseline to follow-up (within-group changes) and differences between the study groups simultaneously, while also accounting for the group-by-time interaction as well as any covariates and interactions that are of scientific interest. An appropriate covariance matrix (eg, autoregressive or unstructured) will be selected based on the final data. The Tukey-Kramer multiple comparisons test will be used to determine specific pairwise differences for statistically significant main effects. Some of these models will include the stratification variable of county and confounding variables (as covariates) such as the baseline BMI category, age, gender, and education level. Some of the models that include physical activity as the dependent variable will be adjusted for wear time. Study variables that will be analyzed using these techniques include the change in minutes of moderate-to-vigorous physical activity. Pearson correlation analysis will be performed to assess the relationship between self-reported and measured physical activity.

Distributions of the aforementioned continuous variables will be examined for normality using box plots, normal probability plots, and the Kolmogorov-Smirnov test. Variables that are determined to deviate from a normal distribution will be log-transformed before statistical testing. Nonparametric tests (eg, the Wilcoxon rank-sum test and the Wilcoxon signed-rank test) may also be used to analyze nonnormally distributed data.

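### The stratification factors (county, BMI group) enter only some MVPA models, and the log rule for non-normal variables has no scale, no offset and no stated order relative to the Wilcoxon tests

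*Combined protocol and SAP*

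**What the plan says.** **Endpoint and scale.** Section 3.1: "Primary endpoints are changes in moderate intensity or greater aerobic physical activity from baseline to 6 months and 12 months". Section 8.2 sizes the trial in untransformed minutes: "Assuming a mean difference of 35 (SD 90) minutes in moderate-to-vigorous physical activity between the two groups".

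**Covariates.** Section 5.2 stratifies the blocked randomisation by county and by BMI group (split at 30), and gives as its reason that BMI is related to activity. Section 8.3.2 makes mixed model repeated measures the primary method. It then says that some of the models will contain county, as a stratification variable, and covariates such as baseline BMI category, which it lists among the confounders. It does not say which models.

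**Distribution rule.** Section 8.3.2 names a change score among the analysed variables: "Study variables that will be analyzed using these techniques include the change in minutes of moderate-to-vigorous physical activity". The check is: "Distributions of the aforementioned continuous variables will be examined for normality using box plots, normal probability plots, and the Kolmogorov-Smirnov test". The consequence is mandatory: "Variables that are determined to deviate from a normal distribution will be log-transformed before statistical testing". The alternative is permissive: "Nonparametric tests (eg, the Wilcoxon rank-sum test and the Wilcoxon signed-rank test) may also be used to analyze nonnormally distributed data".

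**Lower limit of the outcome.** Section 4.1 admits people who are "insufficiently active (engaging in moderate-vigorous physical activity< 60 minutes per week", with no minimum, so zero is an eligible value.

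No section gives an offset, says whether visit minutes or change would be logged, or says how a log-scale effect would be reported.

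**The concern.** Both gaps leave the primary MVPA analysis not fully defined in advance.

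**Stratification factors.** Stratifying makes the arms alike on county and BMI group. If those factors predict activity, as the plan says BMI does, a model that leaves them out keeps their variation in the error term. Its standard error for the arm comparison then tends to be too large, and the precision that stratification was meant to buy is lost. Because only some models include the factors, the choice between an adjusted and an unadjusted primary result also stays open until the data are in.

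**Log rule.** Taken literally, the rule cannot be applied to values that the trial admits. Any workable version needs an offset, and the offset decides how much weight goes to people who start near zero. The result would be on a ratio-like scale, while the sample size is in minutes. Section 8.3.3 also makes the cost-effectiveness analysis conditional on a significantly greater increase in MVPA minutes and then computes cost per minute. The test that opens that analysis should therefore be settled.

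**Working it through.** **1. The plan's own figure.** Inputs from Section 8.2: difference 35, SD 90, two-sided 5%, power 80%.
- Effect size: 35/90 = 0.389 (the plan gives 0.388).
- Normal approximation: n = 2 × (1.960 + 0.842)² × (90/35)² = 2 × 7.849 × 6.612 = 103.8, so 104 per arm.
- Exact t calculation: 104.77, so 105 per arm, with power 80.1% at 105.

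The stated 105 per arm reproduces. It applies to a mean difference in untransformed minutes.

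**2. Where the log is defined.** ln(x) exists only for x > 0.
- Visit minutes: zero is allowed by Section 4.1, so ln(0) is needed and does not exist.
- Change: it can be zero or negative, and the log does not exist there either.

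**3. What the offset does.** Take a gain of 35 minutes (the planning difference) from 0 and from 60 (the upper edge of the entry rule), and compute ln[(start + 35 + c)/(start + c)].

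| Offset c | Gain from 0 | Gain from 60 | Ratio |
|---|---|---|---|
| 1 | ln(36/1) = 3.584 | ln(96/61) = 0.453 | 7.9 |
| 10 | ln(45/10) = 1.504 | ln(105/70) = 0.405 | 3.7 |
| no log | 35 | 35 | 1.0 |

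This is arithmetic only and needs no distributional assumption. The same gain in minutes receives a weight that depends on an unstated constant, so the offset can affect the result.

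**4. Order of methods.** The log is required when a variable is judged non-normal. Wilcoxon tests are allowed when data are non-normal. The condition is the same, so nothing says whether Wilcoxon replaces the logged mixed model or only supports it. Nor does a Wilcoxon test give the covariate-adjusted group-by-time comparison of the mixed model.

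**5. Stratification factors.** Section 4.1 lists six counties. With two BMI groups there are 6 × 2 = 12 strata, on average 240/12 = 20 recruited participants each. As main effects the factors need 5 + 1 = 6 parameters, a small number against 240 participants. Both are known before randomisation, so no data need to be added. The gain in precision depends on how much outcome variance the factors explain. The documents do not give that, so no figure is put on it.

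**The case against.** Much of the case on the other side stands, and it limits the point.

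- **A hierarchy exists in part.** The mixed model is named as primary and Wilcoxon is only optional. A reader might infer an inflated false-positive rate from a free choice between log and rank test. The plan does not say that either significant result would count, so that inference is not supported.
- **Wilcoxon has a condition.** It is limited to non-normal data. Only its order relative to the log is missing.
- **Visit minutes are the natural outcome of the mixed model.** With an offset nobody is lost. A reader might infer that participants without an increase would drop out because change is logged. The wording leaves that possible, but nothing shows that it is intended.
- **The log need not cost power.** A reader might infer a large loss. Any such figure rests on assumed zero shares, skewness and within-person correlation, none of which the plan gives. In very skewed data a log or rank analysis can be more powerful than untransformed minutes, so raw versus log is partly a trade-off.
- **Non-normality is not certain.** Minutes are bounded at zero and Section 8.2 reports "The SD of this measure was 90 minutes", so skewness is plausible. The documents do not establish that the check must fail, and they do not say whether raw values, change or residuals would be tested.
- **The covariate question is distinct from the log question.** That is true, but both concern what the primary MVPA model is. Saying that they are separate does not answer why the stratification factors are in only some models.

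**Conclusion.** The point holds in two parts.

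First, county and BMI group are stratification factors, yet the plan does not commit to them in the primary MVPA model. Including them is a free improvement: it uses data already collected and has no material downside.

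Second, the log rule is incomplete. It is undefined for zero minutes and for zero or negative change, it has no stated scale or offset, and its order relative to Wilcoxon is missing. The demonstrated size is the weighting: 7.9-fold with offset 1 and 3.7-fold with offset 10, against equal weight on untransformed minutes. A log-scale estimate would also not be the 35-minute difference on which 105 per arm rests.

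The second part matters only if MVPA is judged non-normal, which is plausible but not established. Its effect on power is unknown because the proportion of zeros is not given. The documents do not support a claim that the planned analysis loses power, loses participants or raises the false-positive rate.

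**What to change.** 1. State in Section 8.3.2 that every primary MVPA model includes county and the BMI group used in the randomisation.
2. Name one primary MVPA analysis before arm-level data are seen. One option is the mixed model on untransformed minutes with empirical (sandwich) or bootstrap standard errors. This keeps the scale of the sample size calculation and needs no normality trigger.
3. Name one sensitivity analysis: either a rank-based analysis or log(minutes + a stated offset).

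**Cost.** SAP wording and model options in SAS, with no new data. The downside is that untransformed minutes can be less powerful than log or rank analyses if the data are very skewed. A sponsor who prefers the log can keep it and still close the gap by fixing three things in advance: that it applies to visit-level minutes, one offset, and the order of the tests.

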8.3.3 ANALYSIS OF THE SECONDARY ENDPOINT(S)

We will investigate potential mediators of the intervention effect (*social support*) using a multiple mediation approach in SPSS, in which all potential mediators are tested simultaneously, using a product of the coefficients method with bootstrapped SEs (5000 samples with replacement). The interest is in estimating the path coefficients, effect sizes, and CIs rather than strict hypothesis testing.

Potential moderators and interactions will be assessed as follows. A variable will be considered a moderator if evidence exists of either qualitative or quantitative interaction with the intervention. We will use a similar analytic approach as in the primary aims; models will include the main effects of intervention (DIAL intervention vs control), the potential moderator (eg, education and neighborhood and environmental features), and the interaction between the two. Evidence of moderation exists if the coefficient of the interaction term is statistically different from zero.

Descriptive analyses of quantitative stakeholder acceptability survey items and content analyses of open-ended items from stakeholder acceptability surveys and focus group transcripts will be conducted to inform future efforts toward sustainability and large-scale dissemination in rural counties.

If, as hypothesized, the DIAL intervention results in significantly greater increases in moderate-to-vigorous physical activity minutes, we will conduct a within-trial cost-effectiveness analysis to determine if the DIAL intervention is cost-effective compared with no active intervention. Perspectives will be those of the health care sector, participants, and society. The time frame will be 6 months. We will estimate the DIAL implementation costs and participants' medical and other costs that may be affected. Effectiveness will be measured by the change in moderate-to-vigorous physical activity minutes and QALY.

Implementation costs will include start-up and ongoing costs necessary to implement the DIAL intervention in other settings and will not include costs of intervention development and research activities (eq. consent process). Start-up costs will include time spent on training by trainers and intervention personnel, materials, space, and other supplies needed. To identify and value the DIAL intervention's ongoing costs, we will develop process maps with intervention staff to identify all key processes (eg. supervision and orienting the participants to the IVR system, preparing, and IVR system tracking and maintenance) and the personnel involved in those processes, and develop a time tracking system to record the time spent in the identified processes. To reduce burden, this system will be used in random weeks by each intervention staff member. County coordinators will also complete time studies to estimate their time. Over the course of the study, we will select 1 week per month randomly for each intervention staff member. Data will then be annualized and combined with hourly wages and fringe benefits of the personnel to value annual personnel costs per activity. Costs of workbooks, handouts and other materials, phone and IVR system, office space, shipping, and others will be tracked and valued using project records or current market prices. Implementation cost data will be summed overall and by intervention-related categories, for example, IVR tracking and maintenance or feedback reporting. We will calculate the average DIAL intervention cost per participant and per minute moderate-to-vigorous physical activity increase.

The implementation costs of participants will include participation time costs, which will be captured with our surveys at baseline, 6 months, and 12 months. Survey questions will ask participants about the time spent reviewing intervention materials and calling into the IVR system and completing surveys and other intervention activities. These activities will also be tracked using the IVR system user data. Time costs will be valued using hourly wages and fringes based on average age and gender groups.

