staff. After all assessment measures are complete, participants will be randomly assigned to a group. Intervention participants will receive orientation to the IVR system and begin the physical activity intervention and the Waitlist Control participants will be encouraged to maintain their normal routine until 6 month assessments. At 6-, 12-, and 18- months, participants will repeat accelerometer wear protocols, 7-Day Physical Activity Recall interviews (by phone), and inperson assessment visits (weight, waist circumference, 2 Minute Step Test, psychosocial surveys) with local staff. Psychosocial surveys will also be distributed at 3-months to a assess potential mediators/ moderators of treatment efficacy. Participants will also complete surveys and exit interviews to assess program satisfaction and solicit feedback for improvement (at 12 months for the intervention arm and 18 months for the waitlist control arm). The wait-control group will be offered the 12 month DIAL intervention (same as intervention arm) after the 6 month assessment.

Throughout the project period, UAB research staff and Office of Community Outreach and Engagement county coordinators will report study progress via weekly emails and Zoom meetings. Surveys and in-depth qualitative interviews with participating Office of Community Outreach and Engagement county coordinators will be held to reflect on barriers and facilitators to implementing IVR-supported cancer prevention interventions in rural Black Belt counties, as well as issues surrounding sustainability and future large scale dissemination.

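### The moderation rule in section 8.3.3 rests on a two-way arm-by-moderator coefficient tied to no visit, so it can mix the month 6 DIAL-versus-untreated contrast with visits that carry no such contrast

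*Combined protocol and SAP*

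**What the plan says.** Section 8.3.3 says that moderation will be analysed much as the primary aims are, and that "models will include the main effects of intervention (DIAL intervention vs control), the potential moderator" and the interaction between the two. The decision rule follows: "Evidence of moderation exists if the coefficient of the interaction term is statistically different from zero". Education and neighborhood or environmental features are the examples of moderators.

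The primary approach is in section 8.3.2: a mixed model for repeated measures at baseline, 6, 12 and 18 months, "also accounting for the group-by-time interaction as well as any covariates and interactions that are of scientific interest". The covariance structure is to be chosen from the final data, with autoregressive and unstructured as examples. Change in MVPA minutes is named as a variable to be analysed this way.

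Section 3.1 keeps the wait-list arm on its normal routine up to the 6-month assessment, and then: "The wait-control group will be offered the 12 month DIAL intervention (same as intervention arm) after the 6 month assessment".

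The synopsis places moderators of treatment efficacy under the fourth exploratory aim; section 3.1 counts them among the secondary endpoints. No power or sample size is given for them.

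**The concern.** In a model with repeated visits, the DIAL effect is a between-arm difference in change, carried by the group-by-time term. Moderation of that effect is therefore an arm-by-moderator-by-visit term. A two-way arm-by-moderator coefficient that is constant over time is a weighted average of the moderator contrast across visits that mean different things:

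- Baseline: before treatment, so zero in expectation.
- Month 6: DIAL against an untreated arm, the contrast of interest.
- Month 12: the first arm has had 12 months of DIAL and the wait list has been offered it for 6.
- Month 18: the first arm is 6 months past the programme and the wait list is finishing it.

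Elsewhere the plan treats month 6 as the control contrast. The sample size uses change to 6 months, the cost-effectiveness comparison has a 6-month time frame, and the synopsis uses later wait-list data to look for replication of the effect. The moderation rule has no such restriction. At stake is the answer to who benefits from DIAL: a moderator of the 6-month effect could be estimated as much smaller than it is and then reported as absent.

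**Working it through.** **The plan's own figure.** Section 8.2: "Assuming a mean difference of 35 (SD 90) minutes in moderate-to-vigorous physical activity between the two groups from baseline to 6 months", two-sided 5%, 80% power. The normal approximation gives n = 2 × (1.960 + 0.842)² × (90/35)² = 103.8, so 104 per arm. The t test needs 105, with power 80.1%. The stated 105 per arm is reproduced.

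**Inputs for moderation.** From the documents: 240 recruited with 15% attrition, leaving 240 × 0.85 = 204; SD 90, taken as the SD of the 6-month change. Assumed, because the documents do not say: a balanced binary moderator measured per person; equal variance at each visit; within-person correlation ρ from 0.3 to 0.7; compound symmetry or AR(1); normal-approximation power.

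**Test on the 6-month change.** SE = 90 × 4/√204 = 25.2 minutes. The moderation detectable with 80% power is 2.80 × 25.2 = 70.6 minutes. A 35-minute moderation has 35/25.2 = 1.39, so power of 28%.

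**Test on a time-constant two-way coefficient.** Generalised least squares weights the visit contrasts by w = V⁻¹1/(1′V⁻¹1), where V is the covariance matrix of the responses and the visit SD is 90/√(2(1 − ρ)). Three examples under compound symmetry, with the 70.6 minutes present at month 6 only:

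- Raw scores at four visits, ρ = 0.5. Each weight is 1/4, so the estimate is 17.7. SE = 90 × √(2.5/4) × 4/√204 = 19.9. Ratio 0.89, power 14%.
- Change at 6, 12 and 18 months. Each weight is 1/3, so the estimate is 23.5. Changes from a shared baseline correlate 0.5, so SE = 90 × √(2/3) × 4/√204 = 20.6. Ratio 1.14, power 21%.
- Change at 6 and 12 months. Each weight is 1/2, so the estimate is 35.3. SE = 90 × √(1.5/2) × 4/√204 = 21.8. Ratio 1.62, power 37%.

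Under AR(1) the month 6 weight is 0.21 to 0.12 with raw scores (falling as ρ rises), 0.56 to 0.83 with three changes, and 0.65 to 0.85 with two changes. Across both structures and ρ 0.3–0.7:

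| Response | Share of effect kept, month 6 only | Power, month 6 only | Power, half persists at month 12 |
|---|---|---|---|
| Raw scores, four visits | 12–25% | 6–23% | 8–44% |
| Change at 6, 12, 18 months | 33–83% | 21–66% | 40–68% |
| Change at 6, 12 months | 50–85% | 37–67% | 68–75% |

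The last cell runs from compound symmetry (0.75 × 70.6/21.8 = 2.43, 68%) to AR(1) with ρ = 0.7 (0.925 × 70.6/24.9 = 2.62, 75%). If the whole moderation persists at month 12, the two-change reading has 81–90% power, against 80% for the 6-month change test.

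**Candidate month 6 estimators are not interchangeable.** At ρ = 0.7, for 70.6 minutes:

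- Raw month 6 contrast: SE = 25.2/√(2 × 0.3) = 32.5, power 58%.
- Change from baseline: SE = 25.2, power 80%.
- Month 6 adjusted for baseline: SE = 25.2 × √(1.7/2) = 23.2, power 86%.

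**The case against.** The strongest reply is that the pooled model is partly an inference. The term list in 8.3.3 leaves out time itself, so it cannot be complete, and 8.3.2 leaves room for further interactions. The primary aim concerns change to 6 and 12 months, which suggests a response excluding month 18 and using baseline only to form the change. This stands as a limit on the size: on that reading half or more of the effect survives, and all of it if the moderation persists to month 12. It does not rescue the rule. No three-way term or visit is specified, and the decision rests on a single arm-by-moderator coefficient. If a three-way term were added under reference coding, that coefficient would describe only the reference visit, so the rule would still need rewording.

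Other replies also stand in part. Compound symmetry, which gives the lowest power for change scores, is not among the structures 8.3.2 names as examples. A 70.6-minute moderation is twice the whole assumed DIAL effect of 35 minutes, and at 35 minutes even the 6-month change test has only 28% power. Environmental moderators come from the RALA, completed per county in six counties, so person-level figures for 204 people do not describe them.

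A reader might go further and infer that real moderators will be missed, that dilution is always to a quarter or a half, or that the sign will reverse because the arms swap roles at month 18. The documents support none of these. The result is attenuation and lost power, not a certain miss. The share kept ranges from 12% to 85% with moderation at month 6 only. Nothing in the documents fixes the later contrasts: they need not be zero, and uptake of the offer may be incomplete. With a quarter of the moderation at month 12 and minus a quarter at month 18, the pooled raw-score estimate was 3.4 to 17.6 minutes: small, but still positive.

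**Conclusion.** The point holds in a limited form. The stated rule does not isolate the DIAL-versus-untreated contrast at month 6, and moderation of the 6-month effect is likely to be attenuated and may be missed. For 70.6 minutes at month 6 only, power falls from 80% to about 6–23%, 21–66% or 37–67%, depending on the response. It does not fall at all if change at 6 and 12 months is analysed and the moderation fully persists at month 12. These figures rest on 204 completers, a balanced person-level binary moderator, SD of change 90, ρ of 0.3–0.7, and compound symmetry or AR(1). They do not extend to county-level RALA moderators.

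A reader might infer that the primary result is at risk; this point does not show that. It concerns the moderator aim only. The correction removes the mixing of visits, but the test remains weak for moderation of realistic size.

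**What to change.** In section 8.3.3, replace the rule with one named estimator. Suggested wording: *Moderation is assessed by the arm-by-moderator effect on 6-month MVPA, adjusted for baseline MVPA. Moderator-specific 6-month DIAL effects are reported with 95% confidence intervals. Any 12-month moderator contrast is presented separately and labelled as post-crossover.*

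If the repeated-measures model is kept, include arm, visit, moderator, all two-way terms and arm-by-moderator-by-visit, and test the arm-by-moderator contrast in change from baseline to month 6. Choose one of the two in advance, since they are different estimators.

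Add a sentence that interaction tests have low power, so the emphasis is on estimates and intervals, and that county-level features rest on six counties. The cost is SAP wording and, in the second option, the added moderator-by-visit terms. No new data are needed.
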